**Figure 9 Guidelines for Obinutuzumab Infusion: First Infusion**

[figure not shown]
IRR = infusion-related reaction.

a All patients should receive full premedication with an oral corticosteroid, antihistamine, and oral analgesic/anti-pyretic prior to the first obinutuzumab infusion. Refer to Section 4.3.2.6 for details.

b Supportive treatment should include acetaminophen/paracetamol and an antihistamine such as diphenhydramine, if not administered within the previous 4 hours. Intravenous saline may be indicated. For bronchospasm, urticaria, or dyspnea, patients may require antihistamines, oxygen, corticosteroids (e.g., 100 mg oral prednisone or equivalent), and/or bronchodilators. For anaphylaxis precautions, see Appendix 9.

**Figure 10 Guidelines for Obinutuzumab Infusions: Second and Subsequent Infusions**

IRR=infusion-related reaction.

a Patients should receive full premedication with an oral corticosteroid, antihistamine, and oral analgesic/anti-pyretic prior to the obinutuzumab infusion. Refer to Section 4.3.2.5 for details. In the case of a recurrent Grade 3 IRR, obinutuzumab may be discontinued at the discretion of the investigator following an individual benefit-risk assessment.

b Patients who experience wheezing, urticaria, or other symptoms of anaphylaxis must receive full premedication prior to all subsequent doses.

#### **4.3.2.2 Idasanutlin**

Study patients will self-administer idasanutlin tablets orally each day with their own choice of fed or fast.

On days when both idasanutlin and obinutuzumab are given, the order of study treatment administration will be idasanutlin followed by obinutuzumab. If vomiting occurs within 15 minutes of taking idasanutlin and all expelled tablets are still intact, another dose may be given and the second dose noted in the drug log. Otherwise, no replacement dose is to be given. In cases where a QD dose of idasanutlin is missed or forgotten, the patient should take the dose as soon as possible, ensuring that the dose is taken within 8 hours of the missed dose with food. Otherwise, the dose should not be taken. On days when patients are scheduled to have blood samples collected for PK assessments, the time of each dose of idasanutlin will be recorded to the nearest minute. Idasanutlin must be stored according to labeled storage conditions.

#### **4.3.2.3 Rituximab**

*Rituximab will be administered by IV infusion at a dose of 375 mg/m^2 on Day 1 of Cycles 1–6 during induction treatment and every other month (i.e., every 2 months) during consolidation treatment.*

*Body surface area (BSA) will be determined at screening and should be used to calculate the dose of rituximab throughout the study unless the patient's weight increases or decreases by > 10% from screening, in which case BSA should be recalculated and used for subsequent dosing. In obese patients (defined as body mass index • 30 kg/m^2), there is no BSA cap and actual body weight, not adjusted weight, is recommended. Empiric dose adjustment for obese patients may be implemented per institutional guidelines.*

*The infusion of rituximab may be split over 2 days if the patient is at increased risk for an IRR (high tumor burden or high peripheral lymphocyte count). Administration of rituximab may be continued on the following day, if needed, for patients who experience an adverse event during the rituximab infusion.*

*If a dose of rituximab is split over 2 days, both infusions must occur with appropriate premedication (see Section 4.3.2.6) and at the first infusion rate (see Table 8).*

*Rituximab infusions will be administered according to the instructions in Table 8.*

*During the treatment period, rituximab must be administered to patients in a setting where full emergency resuscitation facilities are immediately available. Patients should be under close supervision of the investigator at all times.*

*Rituximab should be administered as a slow IV infusion through a dedicated line. After the end of the first infusion, the IV line or central venous catheter should remain in place for • 2 hours in order to administer IV drugs, if necessary. If no adverse events*

occur after 2 hours, the IV line may be removed or the central venous catheter may be de-accessed. For subsequent infusions, the IV line or central venous catheter should remain in place for at least 1 hour after the end of the infusion. If no adverse events occur after 1 hour, the IV line may be removed or the central venous catheter may be de-accessed.

If a patient tolerates the first cycle of study treatment without significant infusion reactions, rituximab may be administered as a rapid infusion (over 60 • 90 minutes) in accordance with local institutional guidelines.

No dose modification for rituximab is allowed. Guidelines for treatment delays or discontinuation are provided in Section 5.1.5.

Premedication with a corticosteroid, analgesic/antipyretic, and antihistamine, as outlined in Section 4.3.2.6, is required to reduce the incidence and severity of IRRs. For anaphylaxis precautions, see Appendix 9.

**Table 8 Administration of First and Subsequent Infusions of Rituximab**

First Infusion (Day 1 of Cycle 1)	Subsequent Infusions

 
• Begin infusion at an initial rate of 50 mg/hr.
 
• If no infusion-related or hypersensitivity reaction occurs, increase the infusion rate in 50-mg/hr increments every 30 minutes to a maximum of 400 mg/hr.
 
• If a reaction develops, stop or slow the infusion. Administer medications and supportive care in accordance with institutional guidelines. If the reaction has resolved, resume the infusion at a 50% reduction in rate (i.e., 50% of rate being used at the time when the reaction occurred).
 
	
 
• If the patient experienced an infusion-related or hypersensitivity reaction during the prior infusion, use full premedication, including 100 mg of prednisone/prednisolone or 80 mg of methylprednisolone or equivalent (until no further IRR occurs); begin infusion at an initial rate of 50 mg/hr; and follow instructions for first infusion.
 
• If the patient tolerated the prior infusion well (defined by an absence of Grade 2 reactions during a final infusion rate of • 100 mg/hr), begin infusion at a rate of 100 mg/hr. If no reaction occurs, increase the infusion rate in 100-mg/hr increments every 30 minutes to a maximum of 400 mg/hr.
 
• If a reaction develops, stop or slow the infusion. Administer medications and supportive care in
 

First Infusion (Day 1 of Cycle 1)	Subsequent Infusions
	accordance with institutional guidelines. If the reaction has resolved, resume the infusion at a 50% reduction in rate (i.e., 50% of rate being used at the time when the reaction occurred).

*IRR = infusion-related reaction.*

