#### **4.3.2.6 Premedication**

Patients should receive premedication as outlined in [Table 9](#).

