**Table 9 Premedication**

Timepoint	Patients Requiring Premedication	Premedication	Administration
Cycle 1, Day 1	• All patients	• Oral corticosteroid a	Administer • 1 hour prior to obinutuzumab or rituximab infusion.
	• All patients	• Antihistamine drug b • Oral analgesic/anti-pyretic c	Administer • 30 minutes prior to obinutuzumab or rituximab infusion.
	• Patients at risk for TLS (e.g., because of bulky disease or renal impairment [creatinine clearance < 70 mL/min])	• Allopurinol or suitable alternative such as rasburicase, along with adequate hydration	Administer prior to obinutuzumab or rituximab infusion.
Cycle 1, Days 8 and 15 (for patients receiving obinutuzumab)	• Patients with no IRR during the previous infusion	• Oral analgesic/anti-pyretic c	Administer • 30 minutes prior to obinutuzumab or rituximab infusion. For patients receiving rituximab who do not experience any IRR with their previous infusion, premedication may be omitted at the investigator's discretion.
Cycles 2 and beyond, Day 1	• Patients with Grade 1 or 2 IRR during the previous infusion	• Antihistamine drug b • Oral analgesic/anti-pyretic c	Administer • 30 minutes prior to obinutuzumab or rituximab infusion.
	• Patients with Grade 3 IRR, wheezing, urticaria, or other symptoms of anaphylaxis during the previous infusion	• Oral corticosteroid a	Administer • 1 hour prior to obinutuzumab or rituximab infusion.
		• Antihistamine drug b • Oral analgesic/anti-pyretic c	Administer • 30 minutes prior to obinutuzumab or rituximab infusion.
	• Patients with bulky disease		
• Patients still at risk for TLS	• Allopurinol or suitable alternative such as rasburicase, along with adequate hydration	Administer prior to obinutuzumab or rituximab infusion.	
Cycles 1 to 6	• All patients receiving idasanutlin	2nd generation anti-emetics like palonosetron, ondansetron, or granisetron	Administer per individual drug prescribing information

Timepoint	Patients Requiring Premedication	Premedication	Administration
Cycles 1 to 6	
 
All patients
 
	
 
No premedication for diarrhea
 
If diarrhea grade 3 or more occurs, loperamide should be given prophylactically for subsequent cycles
 
	

IRR = infusion-related reaction; TLS = tumor lysis syndrome.

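### After a Grade 2 rituximab infusion reaction, Table 8 requires a corticosteroid at the next infusion and Table 9 does not list one; for Grade 1, Table 8 is itself unclear

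*Combined protocol and SAP*

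**What the plan says.** Two parts of the protocol instruct a site on premedication for a rituximab patient who reacted at the previous infusion.

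**Table 8.** Section 4.3.2.3 makes it mandatory: "Rituximab infusions will be administered according to the instructions in Table 8". Its column on subsequent infusions has two bullets that matter here.

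- The first reads: "If the patient experienced an infusion-related or hypersensitivity reaction during the prior infusion, use full premedication, including 100 mg of prednisone/prednisolone", with 80 mg of methylprednisolone or an equivalent as alternatives. It applies until the IRRs stop, goes with a 50 mg/hr start, and names no grade.
- The second begins: "If the patient tolerated the prior infusion well (defined by an absence of Grade 2 reactions". It adds a condition on the final infusion rate (the sign is lost in the extracted text) and allows a 100 mg/hr start. It does not mention premedication.

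**Table 9.** Section 4.3.2.3 also says: "Premedication with a corticosteroid, analgesic/antipyretic, and antihistamine, as outlined in Section 4.3.2.6, is required". Section 4.3.2.6 in turn says "Patients should receive premedication as outlined in" Table 9. From Cycle 2 onward that table has these entries.

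- "Patients with Grade 1 or 2 IRR during the previous infusion" receive an antihistamine and an oral analgesic/antipyretic.
- The oral corticosteroid is added for "Patients with Grade 3 IRR, wheezing, urticaria, or other symptoms of anaphylaxis during the previous infusion" and, in the same block, for bulky disease.
- The administration column names both antibodies and includes a sentence on rituximab alone: "For patients receiving rituximab who do not experience any IRR with their previous infusion, premedication may be omitted" at the investigator's discretion.

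**The concern.** Both tables are current protocol text and both apply to rituximab. A site that looks up premedication under the section of that name finds a row matching a Grade 2 patient exactly. The row lists no corticosteroid and does not point back to Table 8. Following it, the site would give a patient who has already reacted less premedication than the rituximab-specific rule requires, and would create a protocol deviation without knowing it. Section 5.1.2.1 says most rituximab IRRs are Grade 1 or 2, which is where the two tables need to agree. Sites could differ in practice for no clinical reason.

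**Working it through.** The plan states no figure on this point and there is nothing to compute. The check sets the two tables side by side by the worst reaction at the prior rituximab infusion.

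| Prior reaction | Table 8 | Table 9 (Cycle 2 onward) | Result |
|---|---|---|---|
| None | Second bullet, if the rate condition is met; no corticosteroid stated | Analgesic/antipyretic, may be omitted for rituximab | No conflict on the corticosteroid |
| Grade 1 only | First bullet fits (a reaction occurred); second bullet also fits (no Grade 2 reaction), if the rate condition is met | Antihistamine and analgesic/antipyretic | Unclear within Table 8 |
| Grade 2, no special features | First bullet only: full premedication with corticosteroid | Antihistamine and analgesic/antipyretic | **Conflict** |
| Grade 1 or 2 with wheezing, urticaria, other anaphylaxis symptoms or bulky disease | As above, by grade | Corticosteroid added | No shortfall under Table 9 |
| Grade 3 | First bullet: corticosteroid | Corticosteroid added | Agree |
| Grade 4 | Treatment stopped (Section 4.6.2, Table 19) | Treatment stopped | Not relevant |

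1. *Grade 2.* The second bullet of Table 8 is closed to this patient by its own definition, so only the first bullet applies and it requires the corticosteroid. Table 9 does not list it.
2. *Grade 1.* The first bullet is worded for a reaction without a grade. The second is worded so that a patient without a Grade 2 reaction can meet it. If the two bullets are alternatives, a Grade 1 patient may belong to the second, which asks for no corticosteroid.
3. *Precedence.* No text ranks the tables. The sentence in Section 4.3.2.3 that names a corticosteroid defers to Section 4.3.2.6, which is Table 9, so it does not decide the matter.
4. *Direction.* Table 9 does not forbid a corticosteroid. A site that follows Table 8 satisfies both tables; a site that follows Table 9 as written falls short of Table 8.
5. *Dose.* There is no disagreement on the dose when a corticosteroid is given. Footnote a of Table 9 also lists 100 mg of prednisone or prednisolone and 80 mg of methylprednisolone.
6. *Reach.* Only rituximab patients are concerned: the DLBCL bridging cohorts and about 40 DLBCL patients in the expansion phase (Section 3.1.3). The documents give no rate of Grade 2 rituximab IRRs, so the number affected cannot be derived.
7. *Dose finding.* Section 3.1.2.1 counts Grade 3 or 4 non-hematologic events as DLTs and exempts even Grade 3 or 4 IRRs.

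**The case against.** The strongest reply is that Table 9 cannot be used alone. It contains no infusion rates, so staff must open Table 8, where the corticosteroid instruction stands in the same bullet as the 50 mg/hr starting rate. Table 8 is also specific to rituximab, while Table 9 is shared with obinutuzumab and introduced by a softer verb. This stands as an argument that many sites would reach the right answer. It does not remove the conflict, because Section 4.3.2.3 itself sends the reader to Section 4.3.2.6 for premedication.

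A second reply is that making Table 8 prevail presumes what the sponsor meant; Table 9's graded scheme could be the intended one. The documents do not settle intent. For Grade 2, however, Table 8 is the mandatory rituximab rule, and following it breaches neither table.

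Two stronger readings are tempting and are not supported.

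- A reader might infer that the conflict covers Grade 1 as firmly as Grade 2, because the first bullet of Table 8 names no grade. That is an inference from silence. The second bullet can be read as taking Grade 1 patients out of the corticosteroid rule. Equally, it does not mention premedication, so it does not clearly waive it. The Grade 1 case is open.
- A reader might infer that the rapid-infusion option in Section 4.3.2.3 adds a further contradiction, since it does not grade the reactions that rule it out. It does not: the option is discretionary and its conduct is left to local institutional guidelines.

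**Conclusion.** The inconsistency is real and firm for a Grade 2 rituximab IRR without wheezing, urticaria, other anaphylaxis symptoms or bulky disease. For Grade 1 the finding is narrower: Table 8's two bullets overlap, so the required premedication and starting rate are not determined.

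The impact is small. Section 5.1.2.1 says most IRRs occur at the first administration, and Table 8 looks only at the prior infusion. The difference is therefore typically one corticosteroid dose at one infusion. Serious IRRs are described there as uncommon, and Section 4.3.2.3 requires close supervision with resuscitation facilities at hand. Dose finding, the primary endpoint and sample size are unaffected. The point still deserves correction because it concerns a patient-safety instruction in which two binding tables differ.

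The conclusion assumes that the exclusion of Grade 2 reactions in Table 8's second bullet also excludes higher grades, and that bulky disease belongs to Table 9's corticosteroid block, as the layout suggests.

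**What to change.** 1. In Table 9, add one sentence: rituximab patients with a Grade 2 or higher IRR at the previous infusion receive full premedication, including a corticosteroid, per Table 8 until no further IRR occurs. In practice this means Grades 2 and 3, since Grade 4 ends treatment.
2. In Table 8, make the two bullets for subsequent infusions mutually exclusive with one stated grade threshold. It should settle whether a Grade 1 reaction falls under the first bullet (corticosteroid and 50 mg/hr start) or the second (100 mg/hr start). The choice is the sponsor's. Table 9's Grade 1 entry should then match.

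The cost is a few lines of text. For patients, the downside is typically about one extra single corticosteroid dose for each one affected. If the sponsor places Grade 1 under the first bullet, those patients also start the next infusion at the slower rate.

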#### **4.3.2.4 Induction Treatment with Obinutuzumab or Rituximab and Idasanutlin**

[figure not shown]
*Patients will receive 6 cycles of induction treatment consisting of obinutuzumab or rituximab and idasanutlin as outlined in [Table 6](#). For patients with FL enrolled in the bridging cohort(s), obinutuzumab will be given alone at Cycle 1, and the obinutuzumab and idasanutlin combination will be given from Cycles 2 to 6.*

*For patients at increased risk for IRRs (high tumor burden), the first obinutuzumab and rituximab infusion may be split and administered over 2 days. If split, obinutuzumab should be given as 100 mg on Day 1 and 900 mg on Day 2.*

*Please refer to [Section 3](#) for further details.*

**Figure 11 Treatment with Idasanutlin and Obinutuzumab: Schedule of Treatment**

[figure not shown]
*Regimen A: Idasanutlin plus obinutuzumab in escalation phase (excluding FL bridging cohorts) and expansion phase if Regimen A is chosen:*

Patients will receive study treatment every 28 days for up to 6 cycles.

*BID = twice a day; C = cycle; D = day; IV = intravenous; QD = once a day.  
 Note: Patients will receive study treatment every 28 days for up to 6 cycles.*

*Regimen B: Idasanutlin plus obinutuzumab in FL bridging cohorts and expansion phase if Regimen B is chosen:*

[figure not shown]

Patients will receive study treatment every 28 days for up to 6 cycles.

*BID = twice a day; C = cycle; D = day; IV = intravenous; QD = once a day.  
 Note: Patients will receive study treatment every 28 days for up to 6 cycles.*

**Figure 12 Escalation Phase (DLBCL Bridging Cohort[s]) and Expansion Phase with Idasanutlin and Rituximab: Schedule of Treatment**

*Idasanutlin plus rituximab regimen:*

Patients will receive study treatment every 28 days for up to 6 cycles.

*BID = twice a day; C = cycle; D = day; IV = intravenous; QD = once a day.*

*Note: Patients will receive study treatment every 28 days for up to 6 cycles.*

#### **4.3.2.5 Post-Induction Treatment for Patients with FL and DLBCL**

*Please refer to Section 3 for further details.*

#### **4.3.2.6 Premedication**

Patients should receive premedication as outlined in [Table 9](#).

**Table 9 Premedication**

Timepoint	Patients Requiring Premedication	Premedication	Administration
Cycle 1, Day 1	• All patients	• Oral corticosteroid a	Administer • 1 hour prior to obinutuzumab or rituximab infusion.
	• All patients	• Antihistamine drug b • Oral analgesic/anti-pyretic c	Administer • 30 minutes prior to obinutuzumab or rituximab infusion.
	• Patients at risk for TLS (e.g., because of bulky disease or renal impairment [creatinine clearance < 70 mL/min])	• Allopurinol or suitable alternative such as rasburicase, along with adequate hydration	Administer prior to obinutuzumab or rituximab infusion.
Cycle 1, Days 8 and 15 (for patients receiving obinutuzumab)	• Patients with no IRR during the previous infusion	• Oral analgesic/anti-pyretic c	Administer • 30 minutes prior to obinutuzumab or rituximab infusion. For patients receiving rituximab who do not experience any IRR with their previous infusion, premedication may be omitted at the investigator's discretion.
Cycles 2 and beyond, Day 1	• Patients with Grade 1 or 2 IRR during the previous infusion	• Antihistamine drug b • Oral analgesic/anti-pyretic c	Administer • 30 minutes prior to obinutuzumab or rituximab infusion.
	• Patients with Grade 3 IRR, wheezing, urticaria, or other symptoms of anaphylaxis during the previous infusion	• Oral corticosteroid a	Administer • 1 hour prior to obinutuzumab or rituximab infusion.
		• Antihistamine drug b • Oral analgesic/anti-pyretic c	Administer • 30 minutes prior to obinutuzumab or rituximab infusion.
	• Patients with bulky disease		
• Patients still at risk for TLS	• Allopurinol or suitable alternative such as rasburicase, along with adequate hydration	Administer prior to obinutuzumab or rituximab infusion.	
Cycles 1 to 6	• All patients receiving idasanutlin	2nd generation anti-emetics like palonosetron, ondansetron, or granisetron	Administer per individual drug prescribing information

Timepoint	Patients Requiring Premedication	Premedication	Administration
Cycles 1 to 6	
 
All patients
 
	
 
No premedication for diarrhea
 
If diarrhea grade 3 or more occurs, loperamide should be given prophylactically for subsequent cycles
 
	

IRR = infusion-related reaction; TLS = tumor lysis syndrome.

a Treat with 100 mg of prednisone or prednisolone, 20 mg of dexamethasone, or 80 mg of methylprednisolone. Hydrocortisone should not be used because it has not been effective in reducing rates of IRR.

b For example, 50 mg of diphenhydramine.

c For example, 1000 mg of acetaminophen/paracetamol.

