### 3.1.2.1 Definition of Dose-Limiting Toxicity

In this study, a DLT is defined as at least one of the following events occurring during the first cycle (*or the first two cycles in the bridging cohorts for patients with FL who start idasanutlin at Cycle 2*) of treatment and assessed by the investigator as not clearly related to the patient's underlying disease:

- *Any Grade 5 adverse event unless unequivocally due to the underlying malignancy or extraneous causes*
- Adverse event of any grade that leads to a delay of more than 14 days in the start of the next treatment cycle
- Grade 3 or 4 non-hematologic adverse event, with the following exceptions:
  - Grade 3 or 4 IRRs
    - Note that IRRs are not dose-dependent events. They may occur even after a small amount of drug has been administered.
    - Grade 3 diarrhea that responds to adequate therapy within 48 hours
    - Grade 3 nausea or vomiting that occurs in the absence of premedication and responds to adequate therapy within 72 hours
- *Any increase in hepatic transaminase > 3 • baseline and an increase in direct bilirubin > 2 • ULN, without any findings of cholestasis or jaundice or signs of hepatic dysfunction and in the absence of other contributory factors (e.g., worsening of metastatic disease or concomitant exposure to known hepatotoxic agent or of a documented infectious etiology) is suggestive of potential drug induced liver injury (according to Hy's Law) and will be considered a DLT*
- Hematologic adverse events that meet any of the following criteria:
  - Grade 3 or 4 neutropenia in the presence of sustained fever of >38°C (lasting >5 days) or a documented infection
  - Grade 4 neutropenia lasting >7 days
  - Grade 3 or 4 thrombocytopenia *if associated with Grade ≥ 3 bleeding*
  - Grade 4 thrombocytopenia lasting >7 days

Other toxicities that are considered clinically relevant and related to study treatment as determined by the investigator and the Medical Monitor may also be considered DLTs.

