**Table 14 Overlapping Toxicities: Idasanutlin and Obinutuzumab**

Adverse Event	Idasanutlin a 5-Day Dosing (100• 800 mg/day) (n=34)		Obinutuzumab (n=215) b	
	Overall Number of Adverse Events (%)	Grade • 3 Adverse Events (%)	Overall Number of Adverse Events (%)	Grade • 3 Adverse Events (%)
Anemia	24%	24%	16% c	3% d
Neutropenia	27%	27%	36% c	5%• 14% d
Febrile neutropenia	12%	12%	5% d	3% c
Thrombocytopenia	44%	44%	18% d	5%• 8% d
Diarrhea	74%	9%	5%• 8% d	0 d
Nausea	74%	12%	5%• 9% d	0 d
Vomiting	50%	3%	5% d	0 d
Fatigue	38%	3%	13% c	NA

NA = not applicable.

a Data from Phase I single-agent idasanutlin study NP27872; all patients were dosed for 5 days.

b Data from obinutuzumab monotherapy.

c Data from Study BO29563.

d Obinutuzumab Investigator's Brochure.

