**Table 19 Guidelines for Management of Non-Hematologic Toxicities (cont.)**

Event	Action to Be Taken
Diarrhea	
Grade 4 diarrhea: Permanently discontinue study treatment.
 
Grade 2 or 3 diarrhea:
 
 
• If Grade 3 diarrhea occurs between Day 1 and Day 5 of the treatment cycle, withhold study treatment only if diarrhea does not improve to Grade • 2 within 48 hours with appropriate treatment. After dose withheld, if diarrhea improved to Grade • 2, resume obinutuzumab or rituximab at full dose and resume idasanutlin at a reduced dose according to guidelines in Section 5.1.5 for current and subsequent cycles.
 
• If Grade 3 diarrhea is present at the time of the next planned cycle, withhold study treatment. If diarrhea improved to Grade • 2, resume obinutuzumab or rituximab at full dose and resume idasanutlin at a reduced dose according to guidelines in Section 5.1.5 for current and subsequent cycles.
 
 
Management for diarrhea:
 
 
• Initiate treatment at the time of onset.
 
• Administer loperamide 4 mg as loading dose; and up to 2 mg every 4 h or after every unformed stool (for a maximum daily dose of 16 mg), or per institutional standard. For subsequent episodes, use 4 mg QD prophylactic loperamide 30 minutes before subsequent dosing. Encourage patients to self-medicate with loperamide 2 mg should diarrhea recur (up to 2 mg every 4 h or after every unformed stool for a maximum daily dose of 16 mg), or per institutional standard.
 
• Monitor electrolyte levels closely and correct as appropriate.
 
• Administer IV fluids as clinically indicated.
 
• Upon presentation of Grade 3 diarrhea, exclude presence of active infections (e.g., Clostridium difficile). If present, treat infection(s) according to local guidelines.
 

Nausea and vomiting	
 
• Administer second-generation anti-emetics like palonosetron, ondansetron, or granisetron. If vomiting occurs within 15 minutes of
 

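### Tables 9 and 19 give different triggers, and possibly different start times, for prophylactic loperamide, so Grade 2 diarrhea falls under conflicting instructions

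*Combined protocol and SAP*

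**What the plan says.** Section 4.3.2.6 refers sites to Table 9 for premedication. For all patients in Cycles 1 to 6, that table states "No premedication for diarrhea" and then "If diarrhea grade 3 or more occurs, loperamide should be given prophylactically for subsequent cycles".

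Table 19 in Section 5.1.5.1 covers non-hematologic toxicity during induction, which is the same six cycles. Its diarrhea row opens with graded instructions. For Grade 4 the action is "Permanently discontinue study treatment", and a combined heading for Grades 2 and 3 follows. A separate management block then begins "Initiate treatment at the time of onset", gives a therapeutic loperamide schedule, and continues "For subsequent episodes, use 4 mg QD prophylactic loperamide 30 minutes before subsequent dosing". The only grade named in that block concerns infection work-up: "Upon presentation of Grade 3 diarrhea, exclude presence of active infections".

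Section 3.1.2.1 counts Grade 3 or 4 non-hematologic events as DLTs, but exempts "Grade 3 diarrhea that responds to adequate therapy within 48 hours". Section 5.2.3 lists diarrhea of Grade 2 or higher as an adverse event of special interest.

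**The concern.** Loperamide given prophylactically shortly before a dose is premedication, so both tables regulate the same act. They set different conditions for it, and no section gives either table precedence. Sites could reasonably follow either one.

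Section 5.1.3.1 describes diarrhea as the most common adverse event with idasanutlin. In the escalation phase a DLT ends the patient's study treatment (Sections 3.1.2 and 4.6.2) and feeds the modified continual reassessment method (mCRM), with three patients enrolled initially per cohort. In the protocol's own hypothetical run (Section 3.1.2.3), three patients at 250 mg without a DLT lead to 300 mg, while one DLT in three keeps the recommendation at 250 mg. A single event can therefore matter, and it is reasonable to want diarrhea in the DLT window managed under one rule.

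**Working it through.** **The two rules side by side**

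| Element | Table 9 | Table 19 |
|---|---|---|
| Period | Cycles 1 to 6 | Induction (6 cycles) |
| Trigger | Grade 3 or higher | An earlier episode; no grade named |
| Start | Later cycles | Before later dosing; cycle not stated |
| Grade 4 | Inside the trigger | Treatment stopped |

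**Trigger.** Take a patient with Grade 2 diarrhea. Under Table 9 the condition is not met and no prophylaxis is given. Under Table 19, Grade 2 appears in the row's graded headings and the loperamide sentence has no grade limit, so the patient is covered. Because one bullet in that block is expressly tied to Grade 3, the others cannot be assumed to share that limit. The conflict remains even if Grade 1 is left out of Table 19, and even if Table 19 is read as requiring a recurrence first, since Table 9 still gives no prophylaxis at Grade 2.

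**Start.** Idasanutlin is taken on Days 1 to 5 of a cycle. If later dosing in Table 19 includes the remaining doses of the same cycle, the start differs from Table 9. If it means the next cycle, the start agrees. The text does not settle this.

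**Grade 4.** Table 9's trigger includes Grade 4 and looks ahead to later cycles. Table 19 stops treatment at Grade 4, so that part of Table 9 can never operate.

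**Illustrative size.** Table 14 gives idasanutlin diarrhea rates of 74% (any grade) and 9% (Grade 3 or higher) with n=34. Reading them as proportions of patients, the only whole-number counts that round to these figures are:

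- 25/34 = 73.5%, printed as 74%; exact 95% interval 55.6% to 87.1%
- 3/34 = 8.8%, printed as 9%; exact 95% interval 1.9% to 23.7%

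The point rates bound the reach of each reading from above, in that study's patients:

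- *Table 9: at most 3/34.* A patient who stops for Grade 4 diarrhea, or for a DLT in the escalation phase, has no later cycle in which to receive prophylaxis.
- *Table 19: at most 25/34.* This counts every grade and every first episode. Leaving out Grade 1, or requiring recurrence, lowers it. The documents give neither a Grade 2 rate nor a recurrence rate.

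No calculation of a change in DLT probability is possible, because the documents give no effect of prophylaxis on diarrhea severity.

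**The case against.** A reader might infer that the choice of table changes who receives prophylaxis from about 9% to about 74% of this trial's patients, a gap of 22/34, or 65 percentage points. The documents do not support that. The footnote to Table 14 reads "Data from Phase I single-agent idasanutlin study NP27872; all patients were dosed for 5 days". According to Section 1.3.3 and Table 1, that was a solid tumor study using the MBP formulation, whereas this trial gives the optimized SDP formulation with an antibody. The difference between two upper bounds from another study is not an estimate of anything in this one.

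A reader might also infer that dose recommendations depend on which table a site follows. That is not shown. Table 19 starts therapeutic loperamide at onset, and nothing in Table 9 restricts treatment. Within a cycle, the contrast is therefore a pre-dose addition to active treatment, not loperamide against none. The exemption for Grade 3 diarrhea turns on response to therapy within 48 hours, not on prophylaxis. The protocol also accepts some variation between sites: Table 19 allows institutional standards for loperamide treatment, and Section 4.4.1 does so for supportive care generally.

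The same-cycle reading and the any-grade reading of Table 19 are both inferences, though natural ones. The Grade 4 overlap leaves no site with two incompatible actions, because discontinuation removes the later cycle.

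These objections limit the size and consequences of the point. They do not remove the conflict at Grade 2, which follows from the wording of the two tables and needs none of the contested readings.

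**Conclusion.** The inconsistency is real and worth correcting. The two tables set different triggers for prophylactic loperamide, and possibly different starts, with no rule of precedence. The clear case is Grade 2 diarrhea.

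The consequence is less uniform management of an event of special interest that can count as a DLT at Grade 3 or 4. An effect on DLT observations, and through them on the mCRM, is possible but unquantified. The Table 14 figures of 74% and 9% show only that the two triggers can select very different groups. Using them here assumes rates like those in 34 patients on single-agent MBP idasanutlin, and even then they are upper bounds. Sample size, error rates and the primary efficacy analysis are not affected. This is an internal inconsistency in wording, and it carries no view on which rule is clinically right.

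**What to change.** Reconcile Tables 9 and 19 so that both state the same triggering grade and the same start, making explicit whether prophylaxis begins with the remaining doses of the current cycle or with the next cycle. State whether a first episode is enough or a recurrence is needed. Make the wording of Table 9 consistent with the discontinuation at Grade 4 in Table 19. The sponsor decides which rule applies.

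Nothing further is needed on data capture or scope. Section 4.4 and the schedules of activities already require concomitant medications to be recorded, and neither table distinguishes escalation from expansion. The cost is a wording change in two tables at the next amendment, with no extra visits or patients.
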